4.3 Randomization and Stratification

All subjects entered in the study will be centrally randomized at the EORTC Headquarters as described in Section 13.3 of the study protocol. The minimization technique used by the EORTC for random treatment allocation is based on the variance method with semi-random assignment dependent on a preset threshold as implemented by Freedman and White.¹ However, per suggestion of the ICH E9 statistical guidelines, the algorithm has been modified to incorporate a random allocation component in order to ensure an additional 15% of completely random assignments.

In this study, the threshold is set to 3, the total number of stratification factors.

Stratification factors are:

- Regions of the world (North America (USA, Puerto Rico & Canada) vs. Europe and Australia vs. Asia/other regions)
- WHO Performance Status (0 vs. > 0)
- Timing of relapse (< 16 weeks vs. ≥ 16 weeks after the first day of the last TMZ cycle)

4.4 Sample Size

This is a comparative randomized, open label, multicenter, multi-arm, Phase II study. Overall Survival (OS) is the primary endpoint.

Based on a one-sided logrank test, at an overall significance level of 2.5% and a power of 91.7% (accounting for the global testing strategy), a total of 118 deaths per comparison (i.e., monotherapy ABT-414 versus control and combination ABT-414 + TMZ versus control) are needed to detect a Hazard Ratio (HR) equal to 0.54 (i.e., a reduction in the hazard of death of 46%). A median OS of 7 months is expected on the control arm (Arm 3) based on literature review. The target treatment effect is assumed to be the same for both treatment arms (Arm 1 and Arm 2) and corresponds to an increase of median OS

to 12.9 months under proportional hazards. It is assumed that median PFS is 2.6 months on the control arm and 4.8 months on the treatment arms corresponding to an HR of 0.54.

The treatment effect on OS and PFS is generally expected to be positive correlated following historical trends.² Since the interim futility criterion (see Section 4.5 below) is primarily based on a PFS effect, the power of the study increases with the strength of association between PFS and OS. If PFS and OS effects are independent, the overall power of the study is estimated to be approximately 85%. The study is therefore expected to have at least 85% power overall as long as OS and PFS are not negatively correlated.

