8.1 Statistical design

8.1.1 Sample size

This is a comparative randomized open label multicenter/multiarm phase II trial. Overall Survival (OS) is the primary endpoint.

Based on literature review, a median OS of 7 months is expected in the mixed control arm (lomustine or TMZ). Based on a one-sided logrank test, at an overall significance level of 2.5% and a power of 91.7% (accounting for the global testing strategy), a total of 170 deaths (118 per comparison, i.e. monotherapy ABT-414 versus control and combination ABT-414 + TMZ versus control) are needed to detect an increase of median OS to 12.9 months in the treatment arms corresponding to a Hazard Ratio (HR) equal to 0.54 (i.e. a reduction in the hazard of death of 46%). Assuming a monthly accrual of 10 patients during month 1 to 12 and 20 patients per month after 12 months, 240 patients can be recruited within 18 months. A follow-up duration of 13 months after end of accrual is required to observe the 170 deaths.

There will be an interim futility analysis organized after observation of 45 PFS events (see section 8.3).

Provided that PFS and OS effects are independent, the overall power of the study is estimated to be approximately 85%. However, treatment effect on PFS and on OS may reasonably be assumed to be positively correlated, and hence the overall power of the study accounting for the interim analysis is expected to exceed 85%.

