8.2.3.6 Global strategy to control type I error for efficacy endpoints

To meet global regulatory requirements, a multiple testing strategy for the following ordered endpoints will be implemented to control the family-wise type I error (alpha) for comparisons of Arm 1 (ABT-414 + TMZ) versus Arm 3 (TMZ/lomustine) and Arm 2 (ABT-414 alone) versus Arm 3 with respect to overall survival (OS) and the pre-defined secondary efficacy endpoints, namely progression-free survival (PFS), objective response rate (ORR), and OS for patients with EGFR vIII mutation.

The following null hypotheses are considered:

H1: Arm 1 is not superior to Arm 3 in OS.

H2: Arm 2 is not superior to Arm 3 in OS.

H1a: Arm 1 is not superior to Arm 3 in PFS.

H2a: Arm 2 is not superior to Arm 3 in PFS.

H1b: Arm 1 is not superior to Arm 3 in ORR.

H2b: Arm 2 is not superior to Arm 3 in ORR.

H1c: Arm 1 is not superior to Arm 3 in OS among EGFR vIII mutated patients.

H2c: Arm 2 is not superior to Arm 3 in OS among EGFR vIII mutated patients.

[figure not shown]
To maintain the overall type I error control for the study, the following null hypotheses will be tested in a fixed sequence of {H1, H2, H1a, H2a, H1b, H2b, H1c, H2c} in order at a 1-sided 2.5% level of significance. Hypothesis H1 will be tested first at a 1-sided 2.5% level. No further tests will be performed if H1 is not

rejected. Each hypothesis will be tested in order specified above if H1 and all preceding hypotheses show statistically significant results at the 1-sided 2.5% level of significance. Otherwise testing in the fixed sequence will stop.

All other endpoints, e.g., PFS in EGFRvIII mutated, global health/QoL status (GHQs), and neurological disease-free survival (NDFS) are considered exploratory and will be tested at a 2-sided 5% level of significance.

Arm 1 vs. Arm 3

Arm 2 vs. Arm 3

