8.3 Interim futility analyses

At interim analysis one or both of the ABT-414 arms might be discontinued based on lack of efficacy for PFS (Reject H1 in favor of H0) according to RANO criteria assessed by IRC.

It is assumed that median PFS is 2.6 months in the control arm and 4.8 months in the treatment arms corresponding to HR equal to 0.54. Assuming an accrual rate of 10 patients/month and activation phase of one year, at least 45 PFS events should be observed. Analyses will be performed when at least 31 PFS events are observed in each comparison. Treatment arms which did not show a minimum level of efficacy, defined as a computed treatment PFS HR lower than 0.91 will be discontinued. The trial will continue with remaining treatment arm(s) and control. There will be no interruption of accrual for the interim analysis.

Treatment PFS HR will be presented with two-sided 95% CI. However, since efficacy data will be analyzed for futility purpose, an alpha spending of 0.00001 will be allocated to the futility analysis. For the final analyses, efficacy endpoint will be tested at a nominal 1-sided alpha level of 0.02499.

For each of the two treatment arms the probability of stopping for futility at the interim is 7.4% if the true PFS HR is 0.54 and 60% if the true PFS HR is 1.0 (no benefit).

Based on the assumed accrual rates and treatment effects stated above, the interim futility analysis is expected to be performed when 90 randomized patients (30 patients per arm) have completed approximately 4 months of follow-up.

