4.6 Type I Error Adjustment Procedures for Multiple Testing

Although Section 8.2.3.6 of the study protocol dated November 25, 2015, describes a different testing order, the multiple testing strategy was revised per diagram (Figure 2) in version 1.0 of the SAP finalized prior to the interim analysis of efficacy data. Given the clinical importance of an overall survival (OS) benefit in recurrent GBM subjects, comparing first OS of combination arm (ABT-414 + TMZ) vs. control and next OS of ABT-414 monotherapy vs. control, followed by comparison of other secondary efficacy endpoints in a similar sequence, is considered a simple and more clinically relevant approach to test the various study hypotheses. At the final analysis, the treatment effects will be tested at the adjusted significance level mentioned in the previous section. The proposed multiple testing strategy based on the above fixed hierarchical sequence preserves the family-wise type-I error at 1-sided 2.5% level. This change was made by consensus agreement among the study sponsors (EORTC and AbbVie Inc.) without any knowledge of unblinded efficacy data from the trial and prior to interim futility analysis.

To describe the multiplicity adjustment procedure fully, consider the following null hypotheses:

H1: Arm 1 is not superior to Arm 3 in OS.

H2: Arm 2 is not superior to Arm 3 in OS.

H1a: Arm 1 is not superior to Arm 3 in PFS.

H2a: Arm 2 is not superior to Arm 3 in PFS.

H1b: Arm 1 is not superior to Arm 3 in ORR.

[figure not shown]
H2b: Arm 2 is not superior to Arm 3 in ORR.

H1c: Arm 1 is not superior to Arm 3 in OS among EGFR vIII mutated subjects.

H2c: Arm 2 is not superior to Arm 3 in OS among EGFR vIII mutated subjects.

To maintain the overall type I error control for the study, these null hypotheses will be tested in a fixed sequence of {H1, H2, H1a, H2a, H1b, H2b, H1c, H2c}. Hypothesis H1 will be tested first, and no further tests will be performed if H1 is not rejected. Thereafter, each hypothesis will be tested in the order specified if and only if H1 and all preceding null hypotheses are rejected. Otherwise testing in the hierarchical sequence will stop.

Figure 2. Testing Procedure

All other endpoints, e.g., PFS in EGFRvIII mutated, global health/QoL status (GHQs), and neurological disease-free survival (NDFS) are considered exploratory and will be tested at a 2-sided 5% level of significance.

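### The 91.7% power given for both OS comparisons omits the fixed-sequence gate on H2 (ABT-414 alone), whose in-sequence power is about 85–86% before the futility look

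*SAP*

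**What the plan says.** SAP 4.4 gives "a power of 91.7% (accounting for the global testing strategy), a total of 118 deaths per comparison" and spells out that the comparisons are monotherapy versus control and combination versus control. Protocol 8.1.1 has "a power of 91.7% (accounting for the global testing strategy), a total of 170 deaths (118 per comparison" and names the same two comparisons; the protocol summary (Number of patients) repeats this. On the effect size, SAP 4.4 adds: "The target treatment effect is assumed to be the same for both treatment arms (Arm 1 and Arm 2"), which is HR 0.54 for each.

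The testing strategy is a fixed sequence with H1 (Arm 1, OS) first and H2 (Arm 2, OS) second. SAP 4.6: "Hypothesis H1 will be tested first, and no further tests will be performed if H1 is not rejected". Protocol 8.2.3.6: "Hypothesis H1 will be tested first at a 1-sided 2.5% level", and later hypotheses are reached only if all preceding ones are rejected.

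One other power is given. SAP 4.4: "If PFS and OS effects are independent, the overall power of the study is estimated to be approximately 85" percent; Protocol 8.1.1 agrees ("Provided that PFS and OS effects are independent, the overall power of the study is estimated to be approximately 85" percent). SAP 4.4 concludes that this is a lower bound unless OS and PFS are negatively correlated. Protocol 8.3 supplies the futility input: "For each of the two treatment arms the probability of stopping for futility at the interim is 7.4" percent if the true PFS HR is 0.54. Neither document gives a separate power for H2.

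**The concern.** A power that accounts for a fixed sequence should, for the second hypothesis, be the probability that both the first and the second are rejected. Attaching one figure to both comparisons is consistent with the sequence only if that figure already contains the gate. If it does not, the planned power for ABT-414 alone, one of the two primary OS comparisons, is overstated. A later reader of a missing or non-significant H2 result would then underestimate how likely that outcome was under the planned effect. The same question applies to the overall figure of about 85%: does it cover H2?

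**Working it through.** **Inputs.** 118 deaths per comparison, HR 0.54 in both arms and one-sided alpha 0.025 (SAP 4.4); 170 deaths in total (Protocol 8.1.1); 1:1:1 allocation with one control arm (SAP 4.2); futility stop probability 7.4% per arm at PFS HR 0.54, cut-off HR 0.91, 31 PFS events per comparison (Protocol 8.3). The correlation between the two OS statistics is not in the documents and is an assumption.

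**1. Reproduce 91.7%.** Mean of the log-rank statistic = √118/2 × |ln 0.54| = 3.347. Power = Φ(3.347 − 1.960) = Φ(1.387) = 0.9172. This is one test at the full level, with no gate. With the FDA-related alpha of 0.024996 (SAP 4.5) it is still 0.9172.

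**2. Correlation from the shared control.** If each comparison has 118 deaths and the total is 170, control deaths = 2 × 118 − 170 = 66 and each ABT-414 arm has 118 − 66 = 52. Correlation = (1/66)/(1/66 + 1/52) = 0.44. With equal information per arm it is 0.50.

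**3. H2 in sequence, before the look.** P(Z1 > 1.960 and Z2 > 1.960), bivariate normal, both means 3.347:

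| Correlation | H2 in sequence | H1 rejected, H2 tested and not rejected |
|---|---|---|
| 0 | 84.1% | 7.6% |
| 0.44 | 85.6% | 6.1% |
| 0.50 | 85.9% | 5.8% |

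The remaining 8.3% is the chance that H1 fails and H2 is never formally tested. The total chance of not rejecting H2 is therefore about 14%, against the 8.3% implied by 91.7%. Given that H1 is rejected, H2's conditional power is 0.8564/0.9172 = 93% to 0.8593/0.9172 = 94%.

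Using the 66/52 split for the mean as well: |ln 0.54|/√(1/66 + 1/52) = 3.323, giving H1 91.4% and H2 85.0%.

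Simulating the planned trial (80 patients per arm, planned accrual, exponential survival, cut at the 170th death, unstratified log-rank) gave H1 91.8% and H2 85.8% in 60,000 runs. A separate 20,000 runs of the same design gave 91.4% and 85.3%.

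**4. The overall figure of about 85%.** Chance of passing futility = Φ((ln 0.91 − ln 0.54) × √31/2) = Φ(1.453) = 0.927, close to the documents' 1 − 0.074 = 0.926. Then 0.917 × 0.926 = 0.849. One comparison's power times one arm's chance of passing reproduces the stated figure.

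**5. H2 after the look.** Assume PFS and OS effects are independent, as the plan does for its 85%, and that the PFS statistics have the same between-arm correlation as the OS statistics. P(both arms pass) is then 0.871 (correlation 0.44) to 0.873 (0.50).

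- H2 not tested if Arm 1 is dropped: 0.871 × 0.856 = 0.746 to 0.873 × 0.859 = 0.750, about 75%.
- H2 tested directly at 2.5% if Arm 1 is dropped: add (0.926 − 0.871) × 0.917 = 0.051, or (0.926 − 0.873) × 0.917 = 0.048, giving about 80%.

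**The case against.** The best reply is that 91.7% is a per-comparison figure and correct as such. The H2 test has the same 118 deaths, the same HR and the same full 2.5%, and the parenthesis about the testing strategy may mean only that the hierarchy avoids splitting alpha. The first half stands: 91.7% is H2's stand-alone power, and no arithmetic slip is involved. The second half does not rescue the wording. The testing strategy is the fixed sequence itself, and for H2 the gate is the part of it that changes power.

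Some further points stand. The correlation is an assumption, so 85–86% is as precise as the result can be. The documents show no derivation for the 85%; the product in step 4 is a reconstruction, and because the 7.4% applies to each arm, it fits either comparison taken alone. The simulations used an unstratified test, whereas the planned test is stratified. Planned power enters no analysis or decision rule, and the interim report had already gone to the IDMC (SAP 4.5).

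A reader might go further and infer that the design is underpowered, or that the 118 deaths are wrong. The documents do not support that. The count reproduces the stated power for H1, and no target is set for H2's in-sequence power. Nor should the 85% be taken as H2's in-sequence power because it lies near 86%: both documents tie it to the PFS futility look.

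**Conclusion.** The point holds as a minor reporting error. The 91.7% is correct for H1 and as the stand-alone power of each test, but it is not H2's power once the global testing strategy is taken into account. That power is about 85–86% before the futility look if both HRs are 0.54 and the correlation is 0.44–0.50, and 84% at zero correlation. The gap is about 6 percentage points.

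The approximately 85% overall power matches a single ungated comparison after the look. On the plan's own independence assumption, H2 after the look is about 75–80%, depending on how the sequence runs if Arm 1 is dropped. Protocol 8.2.3.6 and SAP 4.6 do not say, although Protocol 8.3 and SAP 4.5 let the trial continue with the remaining arm. A positive PFS/OS correlation would raise these figures, but the claim of at least 85% overall is not shown for H2.

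**What to change.** In SAP 4.4, Protocol 8.1.1 and the protocol summary, state 91.7% as the power for H1 and as the stand-alone power of each test. Give H2's in-sequence power as about 85–86% before the futility look if both HRs are 0.54, with the correlation assumption (0.44–0.50 from the shared control).

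In SAP 4.4 and Protocol 8.1.1, state which comparison the approximately 85% refers to, noting that it matches one comparison including the look. Add H2's power including the look (about 75–80% under PFS/OS independence), together with the assumption about how the sequence proceeds if Arm 1 has been dropped. Giving the 86% without the post-look figure would put it beside the 85% and wrongly suggest that the two comparisons have similar power.

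The cost is wording only. Events, patients, test order and alpha do not change.

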4.5 Interim Futility Analysis

An interim futility analysis is planned when at least 45 PFS events (at least 31 PFS events are observed in each comparison) are observed. At interim analysis one or both of the ABT-414 arms might be discontinued based on lack of efficacy for PFS according to RANO criteria assessed by IRC.

Treatment arms which did not show a minimum level of efficacy, defined as a computed treatment PFS HR lower than 0.91 at the interim, will be discontinued. The trial will continue with remaining treatment arm(s) and control. The decision to discontinue a treatment arm not showing a minimum level of efficacy will be based on a review of the totality of interim data and recommendations made by the IDMC. The interim analysis will be carried out according to the Statistical Considerations section in the study protocol and EORTC Policy 004 on Independent Data Monitoring Committees and Interim Analyses.

On April 28, 2016, AbbVie and EORTC contacted the IDMC chair to request a revision of the interim analysis plan. Taking into account the time that was necessary to collect all MRI scans performed, to perform their central review, to code the resulting data in the EORTC database, and to submit the interim analysis report 4 weeks before the IDMC meeting scheduled on May 23, 2016, both AbbVie and EORTC agreed that it was difficult to present the results concerning the centrally reviewed PFS endpoint at the coming

IDMC meeting. On May 20, 2016, the IDMC Chair considered this request and agreed to a postponement of the report.

In May 2016, both AbbVie and EORTC agreed to maintain the same PFS HR futility boundary of 0.91 as initially planned based on the availability of 45 PFS events. The clinical cut-off date for the revised interim analysis was set as July 01, 2016. All scans from subjects randomized before May 07, 2016 with at least one baseline and one follow-up scan were to be reviewed. The interim futility reports were presented to the IDMC on September 21, 2016 based on an interim database locked on August 16, 2016.

While there was no intent to stop the study for superior efficacy observed based on PFS during the interim analysis, an alpha spending of 0.00001 was allotted to the futility analysis per the recommendation of the US Food and Drug Administration (FDA).

Given that a total of 47 deaths had occurred across Arms 1-3 at the time of the PFS futility analysis, when a fixed Haybittle Peto alpha spending (as implemented in *EAST* 6.3) of 0.00001 is applied to the adjusted nominal significance levels for the final analysis for a range of possible values of the observed information fraction are provided in table below.

No. of OS for 2 Arms at Interim	Nominal Adjusted 1-Sided Alpha at Final OS
26 to 30	0.024996
31 to 37	0.024997

For the purposes of review by the FDA, the final adjusted significance level for each comparison (Arm 1 vs Arm3, and Arm2 vs Arm 3) will be determined at the end of the trial using the same Haybittle Peto spending approach as a function of the actual observed information (ratio of observed deaths at the time of the futility look and final analysis on the treatment and control arms). Furthermore, since the primary efficacy endpoint (OS) was never analyzed during the interim analysis and an alpha penalty is technically unnecessary for a futility interim assessment, no adjustment to the final alpha level will be made for other global regulatory purposes and final analyses will be performed at a full overall 1-sided significance level of 0.025.

4.6 Type I Error Adjustment Procedures for Multiple Testing

Although Section 8.2.3.6 of the study protocol dated November 25, 2015, describes a different testing order, the multiple testing strategy was revised per diagram (Figure 2) in version 1.0 of the SAP finalized prior to the interim analysis of efficacy data. Given the clinical importance of an overall survival (OS) benefit in recurrent GBM subjects, comparing first OS of combination arm (ABT-414 + TMZ) vs. control and next OS of ABT-414 monotherapy vs. control, followed by comparison of other secondary efficacy endpoints in a similar sequence, is considered a simple and more clinically relevant approach to test the various study hypotheses. At the final analysis, the treatment effects will be tested at the adjusted significance level mentioned in the previous section. The proposed multiple testing strategy based on the above fixed hierarchical sequence preserves the family-wise type-I error at 1-sided 2.5% level. This change was made by consensus agreement among the study sponsors (EORTC and AbbVie Inc.) without any knowledge of unblinded efficacy data from the trial and prior to interim futility analysis.

To describe the multiplicity adjustment procedure fully, consider the following null hypotheses:

H1: Arm 1 is not superior to Arm 3 in OS.

H2: Arm 2 is not superior to Arm 3 in OS.

H1a: Arm 1 is not superior to Arm 3 in PFS.

H2a: Arm 2 is not superior to Arm 3 in PFS.

H1b: Arm 1 is not superior to Arm 3 in ORR.

[figure not shown]
H2b: Arm 2 is not superior to Arm 3 in ORR.

H1c: Arm 1 is not superior to Arm 3 in OS among EGFR vIII mutated subjects.

H2c: Arm 2 is not superior to Arm 3 in OS among EGFR vIII mutated subjects.

To maintain the overall type I error control for the study, these null hypotheses will be tested in a fixed sequence of {H1, H2, H1a, H2a, H1b, H2b, H1c, H2c}. Hypothesis H1 will be tested first, and no further tests will be performed if H1 is not rejected. Thereafter, each hypothesis will be tested in the order specified if and only if H1 and all preceding null hypotheses are rejected. Otherwise testing in the hierarchical sequence will stop.

Figure 2. Testing Procedure

All other endpoints, e.g., PFS in EGFRvIII mutated, global health/QoL status (GHQs), and neurological disease-free survival (NDFS) are considered exploratory and will be tested at a 2-sided 5% level of significance.

5.0 Analysis Sets

The following analysis sets will be used for analysis of safety and efficacy endpoints of the study.

- Intention-to-treat (ITT) population will comprise all randomized subjects regardless of whether they received study treatment (ABT-414/TMZ/lomustine). Subjects will be classified and analyzed in the arm they were assigned at the time of randomization. The ITT will be the primary analysis set for efficacy endpoints.
- EGFRvIII-Mutated (Ev3M) population will comprise of a subset of subjects who have EGFRvIII mutated tumors in the ITT. The Ev3M will be used to address the objectives of improvement in OS and PFS among subjects with EGFRvIII mutation.
- Safety population will comprise all randomized subjects who have received at least one dose of study treatment [i.e., one dose of lomustine or TMZ (Arm 3), of ABT-414 (Arm 2), and of TMZ and ABT-414 (Arm 1)]. Subjects will be classified according to treatment received. Thus, a subject randomized to Arm 1 who received TMZ but did not receive ABT-414 will be considered in Arm 3. Subjects allocated to Arm 3 who received at least one dose of ABT-414 and those allocated to Arm 2 who received at least one dose of TMZ will be considered in Arm 1. The safety population will be the primary analysis set for analysis of safety endpoints.
- Per-protocol population will comprise all subjects who are eligible and have received at least one dose of study treatment [i.e., one dose of lomustine or TMZ (Arm 3), of ABT-414 (Arm 2), and of TMZ and ABT-414 (Arm 1)]. A subject will be considered to be eligible if he/she did not have any deviation from the subject entry criteria listed in Section 3 of the protocol. Subjects will be classified and analyzed in the arm they were assigned at the time of

randomization. Reason for ineligibility, treatment, and safety profile of excluded subjects will be reported separately.

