8.2.2 Analysis populations

- ◆ Intention-to-treat population (ITT): All randomized patients will be analyzed in the arm they were allocated by randomization.
- ◆ Per protocol population (PP): All patients who are eligible and have received at least one dose of the study drug (i.e. one dose of lomustine or TMZ (arm 3), of ABT-414 (arm 2) and of TMZ and ABT-414 (arm 1)). Patients will be classified and analyzed in the arm they were assigned at the time of randomization.
- ◆ Safety population (SP): All randomized patients who have received at least one dose of the study drug (i.e. one dose of lomustine or TMZ (arm 3), of ABT-414 (arm 2) and of TMZ and ABT-414 (arm 1)). Patients will be classified according to treatment received.

A patient will be considered to be eligible if he/she did not have any deviation from the patient entry criteria listed in chapter 3 of the protocol. Potential eligibility problems will be assessed by the Clinical Research Physician at time of medical review.

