4.2 Design Diagram

This is a comparative randomized, open label, multicenter, multi-arm, Phase II study. The study will consist of three treatment arms; Arm 1 (ABT-414 plus TMZ), Arm 2 (ABT-414 monotherapy), and Arm 3 (mixed control arm of lomustine or TMZ). Subjects will be randomized in a 1:1:1 ratio at the EORTC headquarters after verification of the eligibility criteria discussed in Section 3 of the study protocol.

Arm 1: Subjects will be treated with ABT-414 1.0 mg/kg IV infusion over 30 to 40 minutes once every 2 weeks in combination with TMZ 150 mg/m² Day 1 to 5, for the first 28-day cycle, with dose escalation to 200 mg/m² in subsequent cycles in case of adequate tolerance and until one of the treatment withdrawal criteria has been met. In this Arm 1 the schedule of clinical and lab assessments follows the cycle of TMZ (a delay of TMZ delays the assessment schedule, withholding ABT-414 does not affect the assessment schedule).

Arm 2: Subjects will be treated with ABT-414 monotherapy 1.0 mg/kg IV infusion over 30 to 40 minutes once every 2 weeks until one of the treatment withdrawal criteria has been met.

Subjects in the control arm (Arm 3) will be treated according to the timing of relapse.

Arm 3A: Subjects relapsing during TMZ treatment or within the first 16 weeks after the first day of the last TMZ cycle will be treated with lomustine 110 mg/m² on Day 1 of every 42-day treatment period. Treatment will continue until one of the treatment withdrawal criteria has been met. Lomustine will be given for a maximum of 1 year.

Arm 3B: Subjects relapsing 16 weeks or more after the first day of the last TMZ cycle will be treated with TMZ 150 mg/m² on Day 1 to 5 for the first 28-day cycle, with dose escalation to 200 mg/m² in subsequent cycles in case of adequate tolerance. Treatment will continue until one of the treatment withdrawal criteria has been met.

Treatment should start within 96 hours from randomization. Treatment will be administered until one of the withdrawal criteria described in Section 5.4 of the study protocol has been met. Treatment at further progression will be according to investigators discretion.

Day 1 of the first cycle will be the first day when the study medication is taken.

A schematic of the study design is shown in [Figure 1](#). The study procedures for each visit are outlined in [Table 1](#).

Figure 1. Study Schematic

[figure not shown]

Table 1. Study Activities

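### The SAP's as-treated safety rule moves any Arm 3 subject given ABT-414 to Arm 1 without requiring that temozolomide (TMZ) was taken, contradicting the Arm 1 definition in the same bullet

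*SAP*

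**What the plan says.** The Safety population bullet of SAP 5.0 does three things.

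- It sets the principle: "Subjects will be classified according to treatment received". Protocol 8.2.2 has the same principle: "Patients will be classified according to treatment received".
- It defines the exposure belonging to each arm: "one dose of lomustine or TMZ (Arm 3), of ABT-414 (Arm 2), and of TMZ and ABT-414 (Arm 1").
- It gives reassignment rules for departures. An Arm 1 subject who took TMZ without ABT-414 moves to Arm 3. For the other two arms one sentence sets the rule. It opens "Subjects allocated to Arm 3 who received at least one dose of ABT-414 and those allocated to Arm 2", and for that second group it reads "those allocated to Arm 2 who received at least one dose of TMZ will be considered in Arm 1".

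Arm 3 is not a TMZ arm. SAP 4.2 describes it as a mixed control, and early relapsers in Arm 3A "will be treated with lomustine 110 mg/m² on Day 1 of every 42-day treatment period".

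SAP 12.0, in its entry on analysis sets, describes AbbVie's approach as reporting subjects in the arm they actually received. EORTC instead keeps subjects in the randomized arm if they started that treatment and reports the others separately.

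**The concern.** The reassignment rule for Arm 3 looks only at ABT-414. The TMZ condition later in the sentence is attached to the subjects allocated to Arm 2. An Arm 3 subject need not have taken any TMZ on study, so the rule can place someone in the combination arm who never received the combination.

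The Safety population is the primary set for the exposure summaries (SAP 9.1 and 9.2), the adverse event tables (SAP 11.2) and the microcystic keratopathy tables (SAP 11.2.1). Setting Arm 1 beside Arm 2 in those tables is how a reader separates the toxicity of the combination from that of ABT-414 alone. A subject treated with ABT-414 only, or with lomustine and ABT-414, does not belong in the Arm 1 column.

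**Working it through.** No sample size, power or alpha figure depends on this point, and the plan states no number to reproduce. The check sets the rule beside the arm definitions in the same bullet, for the exposure patterns that the reassignment sentences cover.

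| Allocated arm | Drugs received | Arm whose definition matches | Arm under the SAP sentence | Agree? |
|---|---|---|---|---|
| 3 | TMZ and ABT-414 | 1 | 1 | yes |
| 3 | ABT-414 only | 2 | 1 | no |
| 3 | lomustine and ABT-414 | none | 1 | no |
| 2 | ABT-414 and TMZ | 1 | 1 | yes |
| 2 | TMZ only | 3 | 1 | no |
| 1 | TMZ only | 3 | 3 | yes |

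Of the three ABT-414 patterns considered for Arm 3, the rule is right for one. The last two rows show a second inconsistency: the same exposure, TMZ without ABT-414, goes to Arm 1 or to Arm 3 depending on the randomized arm, which an as-treated rule should not do.

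The sentence also has no time limit. SAP 4.2 leaves treatment after progression to the investigator, and Protocol 7.2.1.7 names TMZ as a study drug. Read literally, TMZ given to an Arm 2 subject after protocol treatment had ended could trigger reassignment to Arm 1.

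**Size per subject**

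- Inputs: 240 patients (Protocol 8.1.1), randomized 1:1:1 (SAP 4.2). Assumption: nearly all are treated.
- Subjects per arm: 240 / 3 = 80.
- One subject is 1 / 80 = 1.25 percentage points of an arm's event rate.
- That is a ceiling. Adding one subject to 80 whose event rate is p raises the rate by (1 − p) / 81 if the subject has the event and lowers it by p / 81 if not. Either change is at most 1 / 81 = 1.23 points.
- When the subject took ABT-414 only, Arm 2 is one subject short as well, so its rates shift by a similar amount.

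**Number of subjects.** The documents give no count of Arm 3 subjects who received ABT-414 and describe no crossover to it. If nobody switches, the effect is exactly zero.

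**The case against.** The best defence is that the intent is plain. The bullet states the as-treated principle, SAP 12.0 repeats it, and the disputed sentence can be read as a worked example that takes for granted that the Arm 3 subject also had TMZ. A programmer meeting a real case could fall back on the principle. ABT-414 is supplied by AbbVie, may be used only as the protocol indicates (Protocol 5.1.1.3), and is dispensed after the site confirms the randomized arm (Protocol 13.4). The case is therefore an administration error, and zero is the natural expectation. Safety is descriptive, with no p-values or confidence intervals (SAP 11.1).

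The points about frequency and consequence stand. The point about intent stands only in part: the assumed TMZ exposure is not written, and it fails for anyone who took lomustine or who was given ABT-414 in place of the control drug. A specific rule would normally be programmed ahead of a general principle, and this one exists only for these rare cases.

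Three stronger readings are tempting, and the documents do not support them.

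- A reader might infer that the rule is wrong for every Arm 3A subject given ABT-414. It is not: one who took both ABT-414 and TMZ is correctly placed in Arm 1. What decides is the drugs received, not the stratum.
- A reader might take the 60% early-relapse figure in Protocol 1.2 as a measure of the error. It approximates the size of the lomustine stratum (0.60 × 80 = 48 of 80) and says nothing about how many were given ABT-414.
- A reader might expect the TMZ-related rows for Arm 1 to be inflated. SAP 11.2 tabulates relatedness drug by drug, so a subject with no TMZ on study should add no TMZ-related event and would mainly enlarge the denominator, slightly diluting the rate.

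**Conclusion.** The point holds as a small drafting error. The sentence contradicts both the principle and the Arm 1 definition in its own bullet, and it misplaces Arm 3 subjects who took ABT-414 without TMZ and Arm 2 subjects who took TMZ without ABT-414.

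The reach is limited to AbbVie's descriptive safety tables. Efficacy is untouched, because the intention-to-treat and per-protocol sets use the randomized arm. EORTC's safety tables follow a different rule. The size is at most about 1.25 points per misplaced subject, assuming about 80 treated subjects per arm. The number of such subjects is unknown and probably zero or very few, since no crossover is described. This is worth correcting because the correction is cheap, not because a material effect on the results is expected.

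**What to change.** Replace the reassignment sentences in SAP 5.0 with rules that depend only on protocol treatment actually received:

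- both ABT-414 and TMZ: Arm 1;
- ABT-414 with neither TMZ nor lomustine: Arm 2;
- TMZ or lomustine without ABT-414: Arm 3;
- lomustine plus ABT-414 without TMZ: listed separately and not counted in any arm.

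These categories do not overlap, and they cover every combination of the three drugs. Add that a drug started after the end of protocol treatment does not reclassify a subject.

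The cost is one SAP passage and one derivation, with no new data. It should be done before database lock, because a classification rule changed after it is known who switched is harder to defend.
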